8.2 Method of Numbering Subjects and Assigning Subjects to Treatment Cohorts or Randomization

After a subject meets all study eligibility requirements at Screening (refer to Section 7.1 for enrollment procedures), the IRT system will be used by the Investigator (or designee) to randomize the subject to double-blind Induction Therapy on Day 1 (Week 0). Subjects randomly assigned in Cohorts 1 - 3 will receive either KHK4083 (one of three dose levels) or placebo in a 3:1 ratio during Part A of Induction Therapy. Additional subjects (Cohort 4) in a 3:1 ratio will receive the recommended KHK4083 dose or placebo during Part B of Induction Therapy. Subjects who received study medication in Part A are not allowed to participate in Part B.

At the end of Induction Therapy, subjects who meet all study eligibility requirements described in Section 7.4 will start receiving open-label KHK4083 at the same dose for that subject's cohort. Subjects who previously met all study eligibility requirements and entered the LTE will continue to receive KHK4083 or placebo during LTE Therapy phase; subject in the LTE may be eligible for the OLE up to Week 28 as described in Section 6.1.4.

8.3 Blinding During the Double-blind Treatment Period (Induction Therapy and Long-term Extension Therapy)

The subject and Investigator (or investigative site personnel) will not know the treatment to which the subject is randomized during the double-blind Treatment Period. Placebo will be administered by IV infusion to each cohort to ensure blinded treatment. The study is being

blinded to prevent bias in the safety evaluation, in particular the severity grading and causality determinations of AEs. However, at any time during the study, if a medical emergency occurs and subject treatment must be known, the blind may be broken according to the procedure in Section 8.4.

An assigned pharmacist (or qualified designee) at each investigative site will be unblinded and responsible for preparing the appropriate treatment based on the treatment assignment by the IRT system. The unblinded pharmacist (or qualified designee) will ensure that the investigational product administered to each subject is labeled such that the treatment identity cannot be determined.

8.4 Unblinding During the Treatment Period and After Induction Therapy and Long-term Extension Therapy

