Long-term Extension Therapy: Week 12 (First Dose) to Week 52	
Subjects who complete double-blind Induction Therapy (i.e., at least five of six treatments) and have a clinical response or mucosal healing are eligible to continue in double-blind LTE Therapy
 
All subjects who qualify will be given two options: 1) To receive no further treatment and proceed directly to the Induction Therapy Follow-up Period (Week 16 through Week 26); or 2) To continue in double-blind LTE Therapy and receive 10 additional treatments of KHK4083 (at the same dose administered to that subject during Induction Therapy) or placebo as maintenance therapy. Each subject will receive one IV infusion every 4 weeks from Week 12 to Week 48 followed by an End-of-LTE Therapy visit at Week 52, and then proceed to the LTE Therapy Follow-up Period (Week 56 through Week 64). Refer to Section 8.1.4.2 for additional dosing details in LTE Therapy.
 
All other subjects, including those who do not complete double-blind Induction Therapy (non-completers), do not meet the criteria for a clinical response, or do not have mucosal healing at Week 12 will receive no further treatment, and thus enter the Induction Therapy Follow-up Period.
	
The LTE is only active for subjects who entered it prior to approval of Amendment 2. Subjects who sign an ICF under Amendment 2 are eligible for the OLE. Subjects who completed double-blind Induction Therapy (i.e., at least five of six treatments) and had a clinical response or mucosal healing were eligible to continue in double-blind LTE Therapy.
 
All subjects who qualified were to have been given two options: 1) To receive no further treatment and proceed directly to the Induction Therapy Follow-up Period (Week 16 through Week 26); or 2) To continue in double-blind LTE Therapy and receive 10 additional treatments of KHK4083 (at the same dose administered to that subject during Induction Therapy) or placebo as maintenance therapy. Each subject will receive one IV infusion every 4 weeks from Week 12 to Week 48 followed by an End-of-LTE Therapy visit at Week 52, and then proceed to the LTE Therapy Follow-up Period (Week 56 through Week 64).
 
Note: Subjects who already started treatment in the double-blind LTE Therapy will continue to receive KHK4083 or placebo during LTE Therapy. If their UC worsens or flares up to Week 28, they may transition to OLE therapy.
 
Subjects who did not qualify were to have received no further treatment and entered the Induction Therapy Follow-up Period.

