- b: Cohort 4 will receive the recommended dose (1.0, 3.0 or 10 mg/kg) determined from safety assessments of Cohorts 1 - 3 in Part A.
- c: Subjects who complete Induction Therapy, have evaluable total Mayo Clinic scores, and have met the criteria for a clinical response or mucosal healing will have the option to continue in LTE Therapy. Subjects who qualify will receive 10 additional treatments (one IV infusion every 4 weeks) of KHK4083 (at the same dose administered to that subject during Induction Therapy) or placebo. (Note: Subjects administered placebo during Induction Therapy will receive placebo during LTE Therapy).
- C=cohort; LTE=long-term extension; MAD= multiple ascending dose.

[figure not shown]
	Forms			
	Title	Statistical Analysis Plan Template		
	Code	Version	Effective Date	Page
	FRM_ST03_032	01	23 Apr 2015	15 of 53

Figure 2 Study Design Diagram in Protocol Amendment 2

Non-completer (NC) - Subject did not complete Induction Therapy

- a: **For those subjects who enrolled under Amendment #1-** Subjects will be in the study for a total of up to 64 weeks. The double blind treatment period includes Induction Therapy (12 weeks) and LTE therapy (40 weeks). A post treatment follow-up period will be conducted at either Weeks 16, 20 and 26 for subjects who only receive Induction Therapy or at weeks 56, 60 and 64 for subjects who receive both induction and LTE Therapies
- b: Cohort 4 will receive the recommended dose (1.0, 3.0, or 10 mg/kg) determined from safety assessments of Cohorts 1 - 3 in Part A.
- c: Endoscopic Responders (ER) include subjects who met the criteria for clinical response at Week 12 and non-responders (NR) includes subjects who did not meet the criteria of a clinical response at Week 12.
- d: **For those subjects who enroll under Amendment #2-**All subjects who complete the induction period, i.e., (received at least of 5 of the 6 doses of double-blind therapy and have Week 12 sigmoidoscopy results from the central reader) and are eligible to continue on in the study have the option to enter the OLE therapy part of the trial and receive 10 additional treatments of KHK4083 once every 4 weeks from week 12 through week 48 at the same dose used in the cohort that they were enrolled in.

C=cohort; IV=intravenous; LTE=long-term extension; OLE=Open-label Extension; MAD=multiple ascending dose; R=randomization.

	Forms			
	Title	Statistical Analysis Plan Template		
	Code	Version	Effective Date	Page
	FRM_ST03_032	01	23 Apr 2015	16 of 53

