3.2 Sample size justification

Assuming a 15% dropout rate, it is anticipated that approximately 60 subjects will be required to be randomized in order to achieve 51 evaluable subjects in the full analysis set (FAS). In Part A (Cohorts 1 - 3), the sample size is based on the feasibility of the safety and tolerability assessment to recommend starting the treatment of the next cohort of 12 subjects/cohort (9 subjects to receive KHK4083 and 3 subjects to receive placebo). In Part B (Cohort 4) for the treatment of 24 subjects (18 subjects to receive KHK4083 at the recommended dose based on the safety and tolerability in Part A and 6 subjects to receive placebo), the sample size is based on the feasibility of exploratory assessments in efficacy and safety at the recommended dose level. Based on the UCEIS and Mayo Clinic scores and from combining Part A and Part B, it is planned to have approximately a total of 27 randomized subjects receive the recommended dose of KHK4083 and 15 subjects receive placebo.

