3.3 Randomization and blinding

After a subject meets all study eligibility requirements at Screening, the Interactive Response Technology (IRT) system will be used by the Investigator (or designee) to randomize the subject to double-blind Induction Therapy on Day 1 (Week 0). Subjects randomly assigned in Cohorts 1 - 3 will receive either KHK4083 (one of three dose levels) or placebo in a 3:1 ratio during Part A of Induction Therapy. Additional subjects (Cohort 4) in a 3:1 ratio will receive the recommended KHK4083 dose or placebo during Part B of Induction Therapy.

The subject, Investigator (or investigative site personnel) and KHK4083 study team at KKD will not know the treatment to which the subject is randomized during the double-blind Treatment Period. Placebo will be administered by IV infusion to each cohort to ensure blinded treatment. The study is being blinded to prevent bias in the safety evaluation, in particular the severity grading and causality determinations of AEs. However, at any time during the study, if a medical emergency occurs and subject treatment must be known, the blind may be broken according to the procedure described in protocol.

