4.1 General

General descriptive statistics for continuous variables include the n (number of observed values), the mean, standard deviation, median, minimum, and maximum values. For categorical variables, the number and percentage of subjects with a specific level of the variable will be presented. The percentage will be calculated using the subjects with a reported value. Counts of missing subjects will be identified for variables that had one or more subjects with a missing result. Descriptive statistics will be presented by treatment Cohort (KHK4083 dose levels; combined KHK4083; and placebo) and by visit.

Unless there are any notes, the following rules will be applied for all tables and figures;

- Data from placebo subjects in each Cohort will be combined, not depending on treatment period (Double-Blind Induction Therapy, Long-Term Extension Therapy, Open-Label Extension Therapy, or Follow-up).
- In the case that Screening or Baseline is necessary in the tables and figures related to LTE Therapy Period, OLE Therapy Period, or Follow-up Period, the data at Screening or Baseline will be used or displayed.
- Double-Blind Therapy Period will be defined as the period including both Double-Blind Induction Therapy Period and LTE Therapy Period.
- When “Week xx” (xx: number) is necessary, “Week xx” displayed on CRF will be used or displayed.

To explain how data are summarized, the figure showing the relationship between period and dose of Investigational Product is displayed in Figure 3 and the table defining the category is displayed in Table 2.

[figure not shown]
	Forms			
	Title	Statistical Analysis Plan Template		
	Code	Version	Effective Date	Page
	FRM_ST03_032	01	23 Apr 2015	20 of 53

Figure 3 Relationship between Period and Dose of Investigational Product

Subjects who do not move to OLE/LTE Therapy

Subjects who move to OLE/LTE Therapy

[figure not shown]

Table 2 Category in Tables and Figures

	4083 Randomized				Placebo Randomized			
	Cohort 1	Cohort 2	Cohort 3	Cohort 4	Cohort 1	Cohort 2	Cohort 3	Cohort 4
Summary Pattern	Category In Tables and Figures							
Double-Blind Induction Therapy Period	1.0 mg/kg	3.0 mg/kg	10 mg/kg	1.0, 3.0 or 10 mg/kg	Placebo			
Double-Blind Therapy Period ¹⁾								
Double-Blind Therapy Period and Double-Blind Therapy Follow-up Period ²⁾								
LTE Therapy Period								
LTE Therapy Period and Double-Blind Therapy Follow-up Period	1.0 mg/kg	3.0 mg/kg	10 mg/kg	1.0, 3.0 or 10 mg/kg	Placebo ³⁾			

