OLE Therapy Period								
OLE Therapy Period and OLE Therapy Follow-up Period								

1) Double-Blind Therapy Period includes both Double-Blind Induction Therapy Period and LTE Therapy Period.

2) Double-Blind Therapy Follow-up Period includes both Follow-up Periods after Double-Blind Therapy Period and LTE Therapy Period.

3) For subjects randomized to Placebo, they receive 4083 administration during the duration but they are summarized as one category as "Placebo".

Image which shows the relationship between summary pattern and data will be displayed in Figure 4.

Figure 4 Summary Patterns

Forms

Title Statistical Analysis Plan Template

Code

Version

Effective Date

[figure not shown]
Page

FRM_ST03_032

01

23 Apr 2015

21 of 53

General reporting conventions will include the following:

- The baseline value for any measurement is the last value obtained prior to receiving administration of KHK4083 or placebo on Day 1 at Week 0. All nominal time points will be used for analysis; actual assessment times will not be used to reclassify the time point at which a measure was taken.

	Forms			
	Title	Statistical Analysis Plan Template		
	Code	Version	Effective Date	Page
	FRM_ST03_032	01	23 Apr 2015	22 of 53

- Study day: Study day will be calculated relative to the date of KHK4083 or placebo administration (Day 1) as:
 - (If Date of event \geq Date of first investigational product administration) Date of event – Date of first investigational product administration + 1 and
 - (If Date of event $<$ Date of first investigational product administration) Date of event – Date of first investigational product administration

This formula will be used when calculating days to a specific event (i.e., concomitant medication and/or AE start date). A negative study day indicates an event prior to investigational product administration.

- Unless otherwise noted, all percentages will be presented to one decimal place.
- Individual data listings of all data represented on the eCRF will be provided as an appendix to facilitate investigation of the tabulated values and to allow for the clinical review of all variables. All data listings will be sorted by dose Cohort, site-subject number, visit, and time points where appropriate.
- Post-dose data from unscheduled visits will be excluded from the summary tables but included in the data listings.

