6.1 Exposure to investigational product

Subjects who received investigational product are those who have the infusion initiation time recorded, and subjects who completed investigational product are those who have the completion time recorded. The definition of treatment duration in weeks will be derived from the recorded date and time of the IV infusion of investigational product as follow:

- Induction therapy: IV infusion of KHK4083 or placebo once every 2 weeks for a total of 6 treatments. For eligible subjects the first dose date for the Induction therapy is recorded at Day 1 (Week 0) after screening period; the last recorded dose date for the Induction therapy should be recorded at Day 71 (Week 10). Under this condition the treatment duration for the Induction

	Forms			
	Title	Statistical Analysis Plan Template		
	Code	Version	Effective Date	Page
	FRM_ST03_032	01	23 Apr 2015	27 of 53

- therapy is derived as $[(\text{last dose date of the Induction therapy} - \text{first dose date of the induction therapy}) + 1] / 7$, and the results will be expressed in weeks and rounded to the nearest integer.
- Long-term Extension Therapy (LTE): all the subjects who qualify and agreed to continue the treatment will receive 10 additional IV infusions of KHK4083 or placebo once every 4 weeks starting from Week 12 (+/- 7 days). Under this condition the treatment duration for the LTE therapy is derived as $[(\text{last dose date} - \text{first dose date of the LTE therapy}) + 1] / 7$, and the results will be express in weeks and rounded to the nearest integer.
 - Open-label Extension Therapy (OLE): all the subjects who qualify and agreed to continue the treatment will receive up to 10 additional IV infusions of KHK4083 once every 4 weeks starting from the first dose of the OLE therapy [“Week” of the first dose of the OLE therapy is different among subjects: Week 12 (+/- 7 days), Week 16 (+/- 7 days), Week 20 (+/- 7 days), Week 24 (+/- 7 days), or Week 28 (+/- 7 days)]. Under this condition the treatment duration for the OLE therapy is derived as $[(\text{last dose date} - \text{first dose date of the OLE therapy}) + 1] / 7$ results will be expressed in weeks and rounded to the nearest integer.

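### Open-label extension safety displays label KHK4083-treated subjects as Placebo, and the whole-study TEAE overview merges their placebo-time and drug-time events

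*SAP*

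**What the plan says.** Treatment in the OLE is KHK4083 only. Protocol 8.2 says that eligible subjects "will start receiving open-label KHK4083 at the same dose" as their cohort, whichever arm they were randomised to. SAP 6.1 says that OLE subjects "will receive up to 10 additional IV infusions of KHK4083".

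The display rule goes the other way. SAP 4.1 states for all tables and figures: "Data from placebo subjects in each Cohort will be combined, not depending on treatment period", and it lists the OLE among those periods. Footnote 3 to Table 2 in the same section reads: "For subjects randomized to Placebo, they receive 4083 administration during the duration but they are summarized as one category as" Placebo.

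The footnote can only describe the OLE. In the double-blind long-term extension (LTE), SAP 3.1 (Figure 1, footnote c) says: "Subjects administered placebo during Induction Therapy will receive placebo during LTE Therapy".

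The safety sections follow this rule:

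- SAP 8.1 describes the OLE and LTE TEAE summaries as KHK4083 dose levels against placebo. It counts an event as treatment-emergent from the first dose of any investigational product.
- SAP 8.2 and 8.4 name a Placebo column for OLE laboratory and ECG summaries. SAP 8.3 gives vital-sign changes the laboratory format.
- SAP 9.2 gives the columns of Table 14.3.1-1.1 as, for example, the three doses, Placebo and All.

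SAP 4.2 says that subjects are analysed by the treatment they actually received. It does not say how this fits with Table 2.

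**The concern.** A column headed Placebo in a phase with no placebo treatment will be read as a control. In the OLE TEAE, laboratory, vital-sign and ECG summaries, on-drug findings from placebo-randomised subjects would sit in that column. The dose would not be shown, and subjects on different cohort doses would be mixed. These subjects would also be missing from the KHK4083 dose columns and from any combined KHK4083 column.

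The whole-study TEAE overview has a second problem. Nothing restarts the count when a placebo subject takes a first KHK4083 dose, so the overall Placebo figure is not a placebo rate. If KHK4083 raises the risk of an event, merging the two periods pulls the Placebo column toward the drug columns.

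**Working it through.** **Planned placebo subjects.** Part A has 3 cohorts × 3 and Part B has 6, so 9 + 6 = 15. This reproduces SAP 3.2: "27 randomized subjects receive the recommended dose of KHK4083 and 15 subjects receive placebo". KHK4083 subjects are 3 × 9 + 18 = 45, and the total is 60.

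**Displays affected by the OLE label, counted by title in SAP 9.4 and 9.5.**

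- TEAE tables 14.3.1-1.4, -2.3, -2.6, -3.3, -4.3, -5.3: 6
- Vital signs table 14.3.4-1.2: 1
- Laboratory tables 14.3.4-2.2, -2.4, -2.6, -2.8, -2.10, -2.12, -2.14, -2.16: 8
- ECG tables 14.3.4-3.2, -3.4, -3.6, -3.8, -3.10: 5
- Total tables: 6 + 1 + 8 + 5 = 20
- Figures 15.4.2, 15.4.4, 15.4.6, 15.4.10, 15.5.2, 15.5.4, 15.5.6, 15.5.8: 8

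**What one placebo-randomised subject contributes to the overall Placebo column.** Induction gives 6 infusions (Weeks 0 to 10). The extension gives 10 (Weeks 12 to 48, every 4 weeks).

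| Path, treatment completed | Placebo infusions | KHK4083 infusions | KHK4083 share |
|---|---|---|---|
| OLE from Week 12 | 6 | 10 | 10/16 = 62.5% |
| LTE, to OLE at Week 16 | 6 + 1 = 7 | 9 | 9/16 = 56% |
| LTE, to OLE at Week 28 | 6 + 4 = 10 | 6 | 6/16 = 37.5% |
| LTE throughout | 16 | 0 | 0% |
| Stops after induction | 6 | 0 | 0% |

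**The column as a whole.** Suppose all 15 receive six induction infusions, *a* enter the OLE at Week 12 and complete it, *b* complete the LTE on placebo, and the rest stop. The KHK4083 share of infusions is 10a / (90 + 10a + 10b). The values of *a* and *b* are assumptions.

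- a = 0: 0%
- a = 5, b = 5: 50/190 = 26%
- a = 5, b = 0: 50/140 = 36%
- a = 15, b = 0: 150/240 = 62.5% (ceiling)

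**Share of OLE subjects displayed as Placebo.** Let r be the OLE entry rate among placebo subjects divided by that among KHK4083 subjects. The documents do not give r. With 15 and 45 randomised, the share is 15r / (15r + 45) = r / (r + 3). For assumed r = 0.5, 1 and 2 this gives 14%, 25% and 40%.

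**Illustration of the bias in the overall counts.** Assume constant hazards, a 12-week event risk of 10% on placebo and 20% on KHK4083, OLE entry at Week 12, and follow-up to Week 64. None of these risks comes from the documents.

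- Placebo throughout: 1 − 0.9^(64/12) = 43%
- Column labelled Placebo: 1 − 0.9 × 0.8^(52/12) = 66%
- KHK4083 throughout: 1 − 0.8^(64/12) = 70%

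The displayed overall difference is about 4 points. The difference at Week 12 is 10 points, and 64 weeks on placebo throughout against KHK4083 would show about 27 points (70 − 43).

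**The case against.** The convention is disclosed. Footnote 3 says openly that these subjects receive KHK4083, Table 2 heads its columns by randomised arm, and each OLE table title names the period. This is true, but a footnote in the SAP does not correct the column heading in the output.

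Keeping former placebo subjects apart is defensible, because they start KHK4083 in the OLE while the others have already had induction doses. This stands. The fault is the label and the missing dose, not the separation.

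Much of the information exists elsewhere. Tables 14.3.1-1.2 to -1.4 split TEAEs by period, and SAP 8.1 can be read as showing periods beside the overall count in the overview itself. AE listings are by dose cohort, SAP 6.1 separates exposure by product, and SAP 7.3 repeats the main efficacy scores by cohort. SAP section 8 also promises safety by dose cohort and overall. An OLE overall column would in fact be all KHK4083-treated subjects, though the SAP does not say so. These points confine the merging to the overall counts of one table. They do not mend the OLE period tables, where the wrong label appears.

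The infusion share is not a measure of misattributed events, and the ceiling is unlikely: OLE entry is optional, and for earlier entrants "The LTE is only active for subjects who entered it prior to approval of Amendment 2". Both points are accepted, and the range therefore starts at zero. SAP 4.2 may be meant only for misallocated treatment, so the conflict with it is one to clarify.

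The count of 20 tables and 8 figures covers safety only. The general rule also reaches OLE quality-of-life, glucocorticoid and subscore tables, so on that side the scope is if anything understated.

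**Conclusion.** The concern holds: followed as written, the SAP labels on-drug OLE safety data as Placebo and makes the overall Placebo count in Table 14.3.1-1.1 a mixture. It should be fixed. The safety displays affected are 20 OLE tables, 8 OLE figures and that one overview table. At most 15 planned subjects are involved. The actual number depends on OLE uptake, which is not stated, so the shares above are scenarios and not estimates.

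The double-blind tables, the Week 12 proof-of-concept analysis, the Week 52 ANCOVA and the MMRM do not use OLE data and are unaffected. Figures 3 and 4 of the SAP and the table shells were not available. The conclusion rests on the text of SAP 4.1, 8.1 to 8.4 and 9.2.

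**What to change.** - In Table 2 and SAP 4.1 and 8.1 to 8.4, rename the OLE category Placebo to KHK4083 and identify the dose received, at least in the safety summaries.
- State that the OLE overall or All column is all KHK4083-treated subjects.
- In SAP 8.1, remove the comparison with placebo for the OLE and keep it for the LTE.
- In Table 14.3.1-1.1, do not count events with onset after the first KHK4083 dose under Placebo. Either drop the overall Placebo column and rely on Tables 14.3.1-1.2 to -1.4, or assign TEAEs by treatment at onset and show subject-time for each column.
- Change the column-label example in SAP 9.2 to match.
- State that Table 2 governs display categories, and how it fits with the treatment-received rule in SAP 4.2.

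The cost is wording in the SAP and the shells. The treatment-at-onset option adds one derived variable and subject-time, both from dose dates that SAP 6.1 already uses. No new data are needed.

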ALT=alanine aminotransferase; AST=aspartate aminotransferase; BUN=blood urea nitrogen; β-HCG=beta human chorionic gonadotrophin; ; FSH=follicle-stimulating hormone; HIV=human immunodeficiency virus; IGRA=interferon gamma release assay; LDH=lactate dehydrogenase; LTE=long-term extension; OLE=open-label extension; PD=pharmacodynamic(s); PPD=purified protein derivative; RBC=red blood cell; RNA=ribonucleic acid; RT-PCR=Real-time reverse transcription-polymerase chain reaction; SGOT=serum glutamic-oxaloacetic transaminase; SGPT=serum glutamic-pyruvic transaminase; TB=tuberculosis; US=United States; WBC=white blood cell; wr-CRP=wide-range C-reactive protein.

Any clinically important abnormal laboratory values noted at the Screening visit will be recorded as medical history. In addition, in order for the Sponsor to collect additional information about clinically important laboratory abnormalities, at minimum, the following laboratory abnormalities should be captured as appropriate:

- Any laboratory test result that meets the criteria for an SAE;
- Any laboratory abnormality that requires the subject to have study treatment discontinued or interrupted;
- Any laboratory abnormality that requires the subject to receive specific corrective therapy.

All clinically important abnormal laboratory tests occurring during the study will be repeated at appropriate intervals until (1) the value returns to baseline, (2) the value is judged to be clinically acceptable by the Investigator and the Sponsor, or (3) a diagnosis that explains the

abnormal laboratory value is made. When possible, the Investigator should report the clinical rather than the laboratory term (e.g., anemia versus low hemoglobin).

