8.2 Clinical laboratory evaluation

Laboratory values (chemistry, hematology, coagulation profile, and urinalyses) will be numerically described by visit for observed values and change from baseline by treatments (each KHK4083 dose level versus placebo). The numbers and percentages of subjects with high, normal and low laboratory results will be also summarized for each visit by treatments (Placebo, 1.0 mg/kg, 3.0 mg/kg, and 10 mg/kg) and treatment periods (“Double-Blind Therapy Period and Double-Blind Therapy Follow-up Period” and “OLE Therapy Period and OLE Therapy Follow-up Period”). For the laboratory values which have the normal (e.g., below/within above the normal range) or categorical result (e.g., -/±/+), shift tables will display the cross tabulation of the baseline versus the results of the post-baseline by treatments (Placebo, 1.0 mg/kg, 3.0 mg/kg, and 10 mg/kg) and treatment periods (“Double-Blind Therapy Period and Double-Blind Therapy Follow-up Period” and “OLE Therapy Period and OLE Therapy Follow-up Period”).

Means with SDs for numeric parameters among lab values at all visits will be performed graphically by treatments. Mean changes from Baseline will also be performed in the same manner.

Data listings will be generated of all safety lab values that are outside of the normal range. Listing will also be prepared for multiplex-31 assay data.

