8.4 ECGs

Electrocardiogram measurements include heart rate (beats/min), RR interval (msec), PR interval (msec), QRS duration (msec), QT interval (msec), QTc interval (msec) and ECG interpretation. A standard 12-lead ECG will be performed at Screening; during Induction Therapy (predose and at the end of infusion) on Day 1 (Baseline, Week 0), Week 8, and Week 10 and at Week 52 of OLE/LTE Therapy Period. The ECGs will be recorded after the subject has rested for approximately 5 minutes in a supine position.

	Forms			
	Title	Statistical Analysis Plan Template		
	Code	Version	Effective Date	Page
	FRM_ST03_032	01	23 Apr 2015	36 of 53

Summary statistics for the actual ECG parameter values and change from baseline will be provided for each visit. The number and percentage of subjects with elevated QTcF values (> 450 msec, > 480 msec, and > 500 msec) at each scheduled visit (time point) and overall for all post-baseline visits will be presented by treatments (each KHK4083 dose level versus placebo). In addition, the number and percentage of subjects with QTcF values that increase by > 30 msec and > 60 msec from baseline will be presented by treatments at each scheduled visit (time point) and overall for all post-baseline visits. QTcF will be calculated by the Fridericia formula that “(QTcF = QT/(RR)^{1/3})”.

A shift table from baseline to the worst post-baseline values during the treatment period will be provided for QTcF interval. Both scheduled and unscheduled visits during the treatment period will be considered. The following categories will be used: ≤ 450 msec, > 450 and ≤ 480 msec, > 480 and ≤ 500 msec, and > 500 msec.

The numbers and percentages of subjects with reported ‘Abnormal, Clinically Significant Change’ ECG results will be also summarized for each visit by treatments (Placebo, 1.0 mg/kg, 3.0 mg/kg, and 10 mg/kg) and treatment periods (“Double-Blind Therapy Period and Double-Blind Therapy Follow-up Period” and “OLE Therapy Period and OLE Therapy Follow-up Period”).

All ECG parameters will be presented in data listings.

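### A laboratory abnormality seen only at an unscheduled visit enters no laboratory summary or shift table, although the SAP counts unscheduled visits for the QTcF shift table

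*SAP*

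**What the plan says.** The reporting conventions in SAP 4.1 state: "Post-dose data from unscheduled visits will be excluded from the summary tables but included in the data listings". That list has no clause allowing exceptions.

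SAP 8.2 describes two categorical laboratory displays. The first is by visit: "The numbers and percentages of subjects with high, normal and low laboratory results will be also summarized for each visit by treatments". The second is a set of shift tables: "shift tables will display the cross tabulation of the baseline versus the results of the post-baseline by treatments". Neither mentions unscheduled visits. The second does not say whether the post-baseline result is the value at each visit, the last value or the worst value.

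SAP 8.4 handles QTcF differently: "A shift table from baseline to the worst post-baseline values during the treatment period will be provided for QTcF interval", followed by "Both scheduled and unscheduled visits during the treatment period will be considered".

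Protocol 10.6.1 generates additional laboratory data: "All clinically important abnormal laboratory tests occurring during the study will be repeated at appropriate intervals until (1) the value returns to baseline", or until the value is judged acceptable or is explained by a diagnosis. It does not tie these repeats to the visit schedule. Protocol 11.1 confirms that the eCRF has modules for unscheduled visits, so the results will be in the database. Protocol 12.6 expects all data from dosed subjects to enter the summary tables where appropriate.

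**The concern.** Unscheduled blood draws are usually taken because something has prompted them. A rule that removes them from every laboratory table may remove the results most likely to be out of range. Laboratory findings are part of the primary safety endpoint (Protocol 10.1.2), and safety and tolerability is the primary objective of Part A. If the only abnormal result for a subject comes from an unscheduled visit, the laboratory tables show that subject as normal throughout. The listings hold the value but give no rates by dose and placebo, which is what the tables are for. The SAP has already adopted the remedy for one safety variable, QTcF, and gives no reason for stopping there.

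**Working it through.** The plan states no figure to reproduce, so the check sets the rules side by side and then works out the weight of one subject.

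**What each rule does to a laboratory result** (SAP 4.1 and 8.2 as written):

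| Situation | High/normal/low by visit | Shift table |
|---|---|---|
| Abnormal at a scheduled visit, repeated at a scheduled visit | Both values counted | Both eligible |
| Abnormal at a scheduled visit, further out on the same side at an unscheduled visit | First value counted, second not | Second value not eligible, but the category would be the same |
| Abnormal at a scheduled visit, then abnormal on the other side, or a stronger urinalysis result, at an unscheduled visit | First value counted, second not | Second category lost |
| In range at every scheduled visit, out of range only at an unscheduled visit | Subject normal throughout | Subject shows no post-baseline abnormality |

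The last two rows change a cell count. In the second row the category stands, but the extreme value is missing from the descriptive minimum and maximum. Whichever post-baseline value the shift table is meant to use, 4.1 has already removed the unscheduled ones.

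By-visit counts also cannot be added up to give the number of subjects ever abnormal, because one subject may be counted at several visits. No listed laboratory table supplies that number.

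**How far apart scheduled tests are** (Protocol Tables 9-1, 9-2 and 10.4.1-1):

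- Chemistry: every 2 weeks in induction and every 4 weeks in the extension.
- Hematology: the same, but Cohorts 1 to 3 also have Days 2 and 8 after the first dose.
- Coagulation: Screening, Baseline, Week 12 and Week 52. In the extension the gap is 52 − 12 = 40 weeks. A coagulation abnormality found off schedule in that interval reaches no coagulation summary or shift table.

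**Weight of one subject** (planned numbers in Protocol 8.1.4.1 and 12.3.4; SAP 8.2 tabulates by dose level, so Cohort 4 joins the Part A cohort on the same dose):

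- Dose not chosen for Part B: 1/9 = 11.1 percentage points.
- Recommended dose: 9 + 18 = 27, and 1/27 = 3.7 points.
- Pooled placebo: 9 + 6 = 15, and 1/15 = 6.7 points.

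These figures give the weight of a single missed subject. They do not estimate how many subjects would be missed.

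**SAP 4.1 against SAP 8.4.** The first excludes unscheduled post-dose data from the summary tables without qualification, and the second includes them in one. The 8.4 exception is written for the QTcF shift table. The tables of elevated QTcF and QTcF increases have an overall row for all post-baseline visits, and the SAP does not say whether that row includes unscheduled ones.

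**The case against.** Much of the defence stands.

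- Leaving unscheduled values out of by-visit summaries is sound practice, and the high/normal/low table is defined by visit.
- A repeat under Protocol 10.6.1 follows an abnormality already found. If that was at a scheduled visit, it is tabulated, and the repeats may mainly document resolution.
- Excluded values are not lost. They are in the listings, and SAP 8.2 adds a listing of out-of-range values. Abnormalities that qualify as adverse events are reported as such (Protocol 10.6.8), and SAP 8.1 classifies events by onset date, so one found between visits is still counted.
- The shells are in a separate document (SAP 9.7) and may specify the shift-table value.
- A specific section such as 8.4 would normally be read as overriding a general one.

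These points narrow the gap but do not close it. Not every out-of-range result becomes an adverse event, and a shell should not have to contradict the SAP text.

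A reader might infer three stronger things that the documents do not support:

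- *That no required repeat test ever reaches a table.* The protocol does not say where repeats are taken, and one at a scheduled visit is tabulated.
- *That vital signs have the same defect.* SAP 4.1 excludes unscheduled visits, not extra readings. Protocol 10.6.2 describes extra readings alongside infusion monitoring, which takes place at dosing visits. The SAP lists no vital-sign shift table to amend.
- *That dose escalation is affected.* Escalation rests on the Safety Monitoring Committee's review of cumulative safety data (Protocol 6.3), and the unblinded Week 12 table set (SAP 9.4.1) contains no laboratory tables.

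**Conclusion.** The point holds for laboratory data. As written, the high/normal/low and shift tables can understate abnormality, because a worse or first-abnormal value seen only at an unscheduled visit cannot enter them. The categorical effect arises mainly when the scheduled values were all in range. Each such subject is worth 11.1 percentage points in a 9-subject dose group and about 3.7 at the recommended dose, on planned numbers; fewer subjects in the extension would make each weigh more. The documents give no basis for estimating how often it would occur. The conclusion assumes that some unscheduled laboratory tests are taken and recorded under unscheduled visits, which the eCRF provides for, and that the unseen shells follow the SAP text. The conflict between 4.1 and 8.4 needs correcting whatever the frequency. This should be fixed, but it does not undermine the trial's safety review, since listings and adverse event tables remain.

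**What to change.** In SAP 4.1, limit the exclusion to by-visit summaries and figures, and add *unless otherwise stated*, so that 8.4 no longer contradicts it.

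In SAP 8.2, define the laboratory shift table as baseline versus worst post-baseline value (lowest and highest, as relevant to the parameter) in each period, using scheduled and unscheduled visits, as 8.4 does for QTcF. Add an any-post-baseline row to the high/normal/low table, counting each subject once. No change to vital-sign shift tables is needed.

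The cost is a derived worst-value flag, revised shells and their programming and validation; no new data are required. The drawback is that subjects tested more often have more chances to show an extreme value. A footnote giving the number of subjects with unscheduled tests in each group would let readers judge that.
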